#### **4.6. Other Analyses**

Pharmacokinetic analyses will be conducted using the PK Population. Population PK/PD analysis will be analyzed outside of this SAP and will be reported separately.

##### **4.6.1. Pharmacokinetic Concentrations**

Individual and descriptive summaries of VIS649 serum concentrations by timepoint and dose will be provided. Figures of individual serum concentration-time profiles of VIS649 will be created, where the actual time will be plotted on the x-axis.

For participants in the intensive PK population (See current version of Protocol Version for details of the PK substudy) at Months 0 and 11, mean and median concentration time profiles will be calculated by dose and plotted on linear and semi-log scales at Months 0 and 11. The mean profiles will include standard deviation. The number of values above the lower limit of quantification (LLOQ) will be reported in the statistical summaries. Values that are below the limit of quantification (BLQ) will be substituted with zero for the calculation of descriptive statistics of concentration by time point. Missing samples will be reported as no sample ("NS") and excluded from the statistical summaries.

Samples with no actual date and time collected will be excluded from the analysis. No formal statistical comparisons will be performed.

##### **4.6.2. Pharmacokinetic Parameters**

Pharmacokinetic parameter analyses will be conducted using participants from the PK Population or Intensive PK Population.

VIS649 serum concentrations for participants in the intensive PK Population will be analyzed using standard noncompartmental methods. Serum concentration values below the LLOQ will be set to 0 before the peak concentration and set to missing after the peak concentration in the PK evaluation. Individual and summary PK parameters (outlined in [Table 4](#)) will be listed by dose, visit (ie, Month 0 or Month 11) and subject. No formal statistical comparisons will be performed.

##### **4.6.3. Immunogenicity Evaluations**

Anti-VIS649 ADA analyses will be conducted using the Immunogenicity population.

Individual ADA results will be listed by subject and the tabular summarization of ADA results will include the number and proportion of subjects with positive pre-dose ADA response, number/proportion of subjects with positive post-dose ADA response only, and number/proportion of subjects with positive ADA response at any time. The following immunogenicity endpoints will be summarized by group, dose and time point using descriptive statistics.

- Results of a confirmatory ADA assay (positive/negative)
- ADA titers for participants with a positive confirmatory assay
- Results of a neutralizing ADA assay (positive/negative)

No formal statistical comparisons will be performed.

## 4.7. Analyses of Safety Endpoints

Safety analyses will be conducted using the Safety Population and will be summarized by the treatment participants receive.

### 4.7.1. Study Drug Exposure

The duration of drug exposure and compliance will be calculated as specified below and will be summarized by group using descriptive statistics. Duration of drug exposure, compliance and number of doses received for each participant will also be provided in a data listing, flagging participants who withdrew from the study early. In addition, the dose modification (eg, dose interruption during an infusion, missing infusions, et al.), including number of subjects with at least one dose interruption and reasons for interruption will be summarized. A dose is received when there is  $\leq 5$  mL total volume remaining in the bag after infusion.

$$\text{Duration of Exposure} = \text{Last Dose Date} - \text{First Dose Date} + 30 \text{ Days}$$

$$\text{Compliance} = \text{Number of Doses Received}/12$$

$$\text{Percent Compliance} = 100 * (\text{Number of Doses Received}/12)$$

### 4.7.2. Adverse Events

All AEs will be coded using the MedDRA coding system and displayed in tables and data listings using system organ class and preferred term (PT). Severity is assigned by the investigator as mild, moderate or severe.

Analyses of AEs will be performed for those events that are considered treatment-emergent, defined as any AE with an onset date on or after the start of study treatment, including any events that worsen in severity after the start of treatment.

AEs are summarized by incidence rates; therefore, in any tabulation, a subject contributes only once to the count for a given AE or system organ class. For tabulations by maximum severity, participants will be counted only once for the most severe occurrence of the AE or system organ class.

A summary of AEs will include the number and percentage of participants who experience at least one of the following:

- Treatment-Emergent Adverse Events (TEAEs)
- Treatment-Related TEAEs

- Severe TEAEs
- Severe Treatment-Related TEAEs
- Serious TEAEs
- Serious Treatment-Related TEAEs
- Treatment-Related TEAEs Leading to Study Drug Interruption
- Treatment-Related TEAEs Leading to Study Drug Discontinuation
- Treatment-Related TEAEs Leading to Death

The above categories will be presented by system organ class and PT. In these tabulations, a subject contributes only once to each of the incidence rates for a given system organ class or PT, regardless of the number of episodes, by highest severity or closest relationship.

Additional tabular subgroup presentations of TEAEs by System Organ Class and PT will be included as follows:

- TEAEs by concomitant medication with a frequency of use of  $\geq 5\%$  of the participant population during the Treatment Period
- Treatment-Related TEAEs by concomitant medication with a frequency of use of  $\geq 5\%$  of the participant population during the Treatment Period
- Serious Adverse Events by concomitant medication with a frequency of use of  $\geq 5\%$  of the participant population during the Treatment Period
- TEAEs for participants with comorbidities occurring in 5% or more of overall participants by Treatment Group
- TEAEs by Maximum Severity
- Treatment-Related TEAEs by Maximum Severity

No formal hypothesis-testing analysis of AE incidence rates will be performed.

All AEs occurring on-study (including the screening period) will be listed in by-subject data listings, with a flag indicating treatment emergence.

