10.3.1 Definition of Adverse Event and Adverse Reaction

Adverse Event Definition

 • An AE is any untoward medical occurrence in a participant or clinical study participant, temporally associated with the use of study intervention, whether or not considered related to the study intervention. • An AE would not include information recorded as medical history at screening for preplanned procedures for which the underlying condition was known and no worsening occurred. • NOTE: An AE can therefore be any unfavorable and unintended sign (including an abnormal laboratory finding), symptom, or disease (new or exacerbated) temporally associated with the use of study intervention. • Treatment-emergent AEs (TEAEs) are defined as AEs with an onset date on or after the start of study intervention. In more detail, TEAEs are all adverse events which started after start of study intervention; or if the event was continuous from baseline and was worsening, serious, study intervention-related, or resulted in death, discontinuation, interruption or reduction of study intervention dose. • A suspected adverse reaction is any AE for which there is a reasonable possibility that the study intervention caused the AE. For the purpose of Investigational New Drug safety reporting, “reasonable possibility” means there is evidence to suggest a causal relationship between the study intervention and the AE. Suspected adverse reaction implies a lesser degree of certainty about causality.
Events Meeting the Adverse Event Definition

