
 • Any abnormal laboratory test results (hematology, clinical chemistry, or urinalysis) or other safety assessments (eg, ECG, radiological scans, vital signs measurements), including those that worsen from baseline, considered clinically significant in the medical and scientific judgment of the Investigator (ie, not related to progression of underlying disease). It is the Investigator’s responsibility to review the results of laboratory tests for each individual participant as they become available. This review will be documented by the Investigator’s dated signature on the laboratory report. The Investigator may repeat the laboratory test or request additional tests to verify the results of the original laboratory tests. • Exacerbation of a chronic or intermittent pre-existing condition including either an increase in frequency and/or intensity of the condition. • New conditions detected or diagnosed after study intervention administration even though it may have been present before the start of the study. • Signs, symptoms, or the clinical sequelae of a suspected drug-drug interaction. • Signs, symptoms, or the clinical sequelae of a suspected overdose of either study intervention or a concomitant medication. Overdose per se will not be reported as an AE/SAE unless it is an intentional overdose taken with possible suicidal/self-harming intent. Such overdoses should be reported regardless of sequelae.

Events NOT Meeting the Adverse Event Definition

 • Any clinically significant abnormal laboratory findings or other abnormal safety assessments which are associated with the underlying disease, unless judged by the Investigator to be more severe than expected for the participant’s condition. • The disease/disorder being studied or expected progression, signs, or symptoms of the disease/disorder being studied, unless more severe than expected for the participant’s condition. • Medical or surgical procedure (eg, endoscopy, appendectomy): the condition that leads to the procedure is the AE. • Situations in which an untoward medical occurrence did not occur (social and/or convenience admission to a hospital). • Anticipated day-to-day fluctuations of pre-existing disease(s) or condition(s) present or detected at the start of the study that do not worsen.

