10.3.3 Recording and Follow-Up of Adverse Event and/or Serious Adverse Event

Adverse Event and Serious Adverse Event Recording
 
 • When an AE/SAE occurs, it is the responsibility of the Investigator to review all documentation (eg, hospital progress notes, laboratory reports, diagnostics reports) related to the event. • The Investigator will then record all relevant AE/SAE information in the eCRF. • It is not acceptable for the Investigator to send photocopies of the participant’s medical records in lieu of completion of the AE/SAE CRF page. • There may be instances when copies of medical records for certain cases are requested. In this case, all participant identifiers, with the exception of the participant number, will be redacted on the copies of the medical records before submission. • The Investigator will attempt to establish a diagnosis of the event based on signs, symptoms, and/or other clinical information. Whenever possible, the diagnosis (not the individual signs/symptoms) will be documented as the AE/SAE.

Assessment of Intensity
 
The Investigator will make an assessment of intensity for each AE and SAE reported during the study and assign it to one of the following categories:
 
 • Mild: An event that is easily tolerated by the participant, causing minimal discomfort and not interfering with everyday activities. • Moderate: An event that causes sufficient discomfort and interferes with normal everyday activities. • Severe: An event that prevents normal everyday activities. An AE that is assessed as severe should not be confused with a SAE. Severe is a category utilized for rating the intensity of an event; and both AEs and SAEs can be assessed as severe. 
An event is defined as ‘serious’ when it meets at least one of the predefined outcomes as described in the definition of an SAE, NOT when it is rated as severe.

Assessment of Causality
 
The Investigator is obligated to assess the relationship between study intervention and each occurrence of each AE/SAE. Assessment of causal relationship of an AE to the study intervention is defined as follows:
 
 • Related: There is a reasonable possibility of a temporal and causal relationship between study intervention and the AE.

- **Not Related:** There is no temporal or causal relationship between study intervention and the AE.

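### SAP 4.7.2 narrows the protocol's definition of a treatment-emergent AE for events continuing from baseline, without declaring it; the number of events affected is probably small

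*SAP*

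**What the plan says.** Protocol 10.3.1 defines TEAEs in two steps. The first sentence uses onset alone: "AEs with an onset date on or after the start of study intervention". The next sentence, offered as the detail, adds an event that was "continuous from baseline and was worsening, serious, study intervention-related, or resulted in death, discontinuation, interruption or reduction of study intervention dose".

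SAP 4.7.2 keeps the onset rule but has a single extension for earlier events: "any AE with an onset date on or after the start of study treatment, including any events that worsen in severity" after treatment starts. Severity there is the investigator's three-level rating of mild, moderate or severe.

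The flag decides what is tabulated. SAP 4.7.2 states: "Analyses of AEs will be performed for those events that are considered treatment-emergent". Its summary rows cover all TEAEs and those that are treatment-related, severe or serious, plus treatment-related TEAEs leading to interruption, discontinuation or death. Other AEs reach the listings: "All AEs occurring on-study (including the screening period) will be listed in by-subject data listings, with a flag indicating treatment emergence".

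SAP Section 5 names one major change from the protocol, the interim efficacy analysis. It does not mention the TEAE definition.

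**The concern.** AEs are the primary safety endpoint (protocol Table 3), and the TEAE flag is the gate to nearly every AE table. If the two documents set that gate differently, the same record can be counted or not depending on which document the programmer follows, and the study report may not match the protocol without explanation.

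Severity does not stand in for the triggers that the SAP leaves out. Protocol 10.3.3 separates the two ideas: "An AE that is assessed as severe should not be confused with a SAE". Protocol 8.3.2 records seriousness, severity, relationship and action taken as separate items. A moderate event can lead to a hospital admission, or come to be judged related, and still be rated moderate.

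The narrower rule also sits oddly with SAP 3.10. That section imputes partial onset dates so that events lean towards treatment-emergent, and treats a missing relationship as related and a missing severity as severe. Yet an event that the investigator actually judged serious or related can lose its flag because its severity level did not change.

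**Working it through.** The documents state no figure for this point, so the check compares the two rules.

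**Triggers for an event continuing from baseline**

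- Protocol 10.3.1 has seven alternatives: worsening, serious, related, death, discontinuation, interruption, dose reduction.
- SAP 4.7.2 has one: worsening, narrowed to severity.

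**Case by case**

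| AE record | Protocol 10.3.1 | SAP 4.7.2 |
|---|---|---|
| Onset on or after first dose | TEAE | TEAE |
| Continuing from baseline, severity level rises | TEAE | TEAE |
| Continuing, no rise in severity, becomes serious or is judged related | TEAE | not a TEAE |
| Continuing, no rise in severity, leads to death or a dosing change | TEAE | not a TEAE |
| Continuing, none of these | not a TEAE | not a TEAE |

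The documents part in the third and fourth cases.

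**Which SAP rows are exposed**

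- The all-TEAE row loses every such event.
- The serious row loses those that are serious.
- The treatment-related row loses those judged related.
- The interruption, discontinuation and death rows are confined to treatment-related TEAEs. They lose an event only if it is also judged related. An unrelated continuing event that stops dosing is absent from them under either definition.

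**Can such records exist?** Protocol 8.3.1 points both ways. It collects AEs from consent onwards, but also sends occurrences between consent and first dose to the medical history page and not the AE page. The Schedule of Assessments marks AE monitoring at screening, and SAP 4.7.2 expects screening-period AEs in its listings with a treatment-emergence flag. The SAP therefore plans for pre-dose AE records, which are the records on which the rules differ.

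**Size**

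The documents give no expected AE rates, so the number reclassified has to be assumed. With about 36 participants per arm (protocol 9.4.2), k reclassified participants move an arm's rate by k/36:

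- k = 0: no change
- k = 1: 1/36 = 2.8 percentage points
- k = 2: 2/36 = 5.6 percentage points

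**The case against.** The strongest reply is that the data flow leaves little for the two rules to disagree about. Under the medical-history rule in protocol 8.3.1, most pre-dose occurrences never become AE records. If one flares on treatment, protocol 10.3.1 makes that an AE in its own right: "Exacerbation of a chronic or intermittent pre-existing condition including either an increase in frequency and/or intensity of the condition". It would enter with a post-dose onset and meet the SAP's onset clause. This stands, and it is why the affected number is probably small. It also answers the inference that worsening in frequency alone is lost, since the same sentence covers frequency. It does not empty the set, because 8.3.1 also collects AEs from consent and the SAP expects screening-period AEs.

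A reader might also infer that the excluded events survive only in listings. The documents do not support that for events that affect dosing or participation. SAP 4.1 tabulates discontinuations with reasons, and SAP 4.7.1 summarises dose interruptions with reasons. Neither is limited to TEAEs.

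Three further points have some weight:

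- The protocol definition is itself uneven. Its first sentence, read alone, is narrower than the second.
- Some on-treatment occurrences in unworsened conditions, such as elective admissions, are not AEs at all (protocol 10.3.2), so they fall outside both rules.
- The SAP refers to a current protocol version with a Month 16 visit and about 100 sites, while the protocol supplied has Month 15 and about 80. Whether a later version kept this TEAE wording cannot be seen. Section 5 claims to summarise only the major change, so its silence on a smaller one is modest evidence.

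AE analyses are descriptive, with no hypothesis tests, so no formal inference is at risk.

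**Conclusion.** The two definitions differ, and the difference is undeclared. The exposed set is narrow: an AE recorded with pre-dose onset that becomes serious, is judged related, or leads to death or a dosing change on treatment, without a rise in severity level. Such an event drops out of the SAP's all-TEAE row and, where applicable, its serious and treatment-related rows. It drops out of the interruption, discontinuation and death rows only if it is also judged related.

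It may be tempting to conclude that every baseline event that turns serious or stops dosing vanishes from the safety tables. That goes too far. Many such events will also rise in severity, or will be entered as new on-treatment AEs, and both kinds are counted under either rule.

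The number affected cannot be computed. The 2.8 points per participant is plain arithmetic on about 36 per arm and is not an estimate of bias. The conclusion assumes that some pre-dose AE records exist and that the protocol supplied still governs the TEAE wording. Efficacy results are untouched.

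**What to change.** In SAP 4.7.2, derive the TEAE flag for the final tables from protocol 10.3.1 as worded: onset on or after the start of study intervention, or "continuous from baseline and was worsening, serious, study intervention-related, or resulted in death, discontinuation, interruption or reduction of study intervention dose". Protocol 8.3.2 already puts seriousness, relationship, action taken and outcome on the eCRF, so no new data are needed. If the sponsor prefers the narrower rule, SAP Section 5 should declare and justify it.

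The two statements in protocol 8.3.1 should be reconciled at the same time, so that it is clear whether an event starting between consent and first dose belongs on the AE page or the medical history page. Without that, the flag's result will depend on how each site read the section.

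The cost is one flag derivation and slightly higher TEAE counts. The SAP states that it was amended after the interim efficacy analysis, so the final tables are the ones that matter.

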#### 4.7.3. Laboratory Data

Clinical laboratory values will be expressed using the Conventional Units and graded using Common Terminology Criteria for Adverse Events (CTCAE) criteria for applicable parameters.

The actual value and change from baseline (Day 1 Pre-infusion) to each on-study evaluation and to the last evaluation on study will be summarized for each clinical laboratory parameter,

including hematology, chemistry, and urinalysis. In the event of repeat values, the last non-missing value per study day will be used.

Tables presenting shift in CTCAE grade from baseline to worst and baseline to last on-study values may be presented for applicable hematology and clinical chemistry parameters.

All laboratory data will be provided in data listings. A data listing will be presented for all abnormal laboratory values.

#### 4.7.4. Vital Signs and Physical Examination

The actual value and change from baseline (Day 1 Pre-infusion) to each on-study evaluation will be summarized for vital signs.

Vital signs will include a derived measurement of Mean Arterial Pressure (MAP):

$$MAP = \text{Diastolic Pressure} + 1/3(\text{Systolic Pressure} - \text{Diastolic Pressure})$$

Where pressure = blood pressure (mm Hg).

The number and percentage of participants who experience a clinically significant vital sign post-baseline will be summarized. Clinically significant vital signs will be summarized as follows (increases and decreases are from baseline):

- Systolic Blood Pressure (SBP) < 90 mmHg and Decrease  $\geq$  20 mmHg
- SBP > 180 mmHg and Increase  $\geq$  20 mmHg
- Diastolic Blood Pressure (DBP) < 50 mmHg and Decrease  $\geq$  10 mmHg
- DBP > 105 mmHg and Increase  $\geq$  10 mmHg
- SBP  $\geq$  140 mmHg and DBP  $\geq$  90 mmHg
- Heart Rate (HR) < 50 bpm and Decrease  $\geq$  15 bpm
- HR > 120 bpm and Increase  $\geq$  15 bpm

Vital sign measurements will be presented for each participant in a by-group by-participant data listing where results meeting the above clinically significant criteria will be identified.

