5.2 Exclusion Criteria

Participants are excluded from the study if they meet any of the following criteria:

1. Participant has secondary forms of IgAN as defined by the treating physician (eg,, Henoch-Schönlein purpura, minimal change disease with IgA deposits, infection associated IgAN or IgAN associated with hepatic cirrhosis).
2. Participant has co-existing CKD, other than IgAN.
3. Participant has evidence of additional pathological findings in the kidney biopsy (eg, diabetic kidney disease, membranous nephropathy or lupus nephritis lupus). However, hypertensive vascular changes are acceptable.
4. Participant has kidney biopsy MEST or MEST-C score of T2 or C2 from the Oxford IgAN classification schema. If MEST-scoring was not performed, the presence of $> 50\%$ tubule-interstitial fibrosis or crescents in $> 25\%$ of glomeruli is exclusionary.
5. Participant has nephrotic syndrome, defined for this purpose as 24-hour urine protein > 3.5 g with concurrent hypoalbuminemia (serum albumin < 2.5 g/dL), hyperlipidemia (total cholesterol > 350 mg/dL) and edema.
6. Participant has received a solid organ transplant, including kidney.
7. Participant has received bone marrow or hematologic stem cell transplantation.
8. Participant is currently receiving systemic immunosuppression (excluding topical, ophthalmic, per rectum or inhaled corticosteroids).
9. Participant has received systemic steroids within the 12 weeks prior to initial screening.
10. Participant has received treatment with 2 or more systemic immunosuppressive agents within 2 years prior to initial screening.
11. Participant has chronic infectious diseases (eg, chronic urinary tract infection, chronic sinusitis, bronchiectasis, active pulmonary or systemic tuberculosis, chronic viral HCV or hepatitis B virus or HIV infection).

12. Participant has a known allergy or intolerance to any component of the study intervention.
13. Participant has acute infectious disease at the time of screening. Participants may be rescreened following resolution of acute infection (such as urinary tract infection or respiratory tract infection), provided there is no evidence of an immunosuppressive condition that predisposed the participant to this infection.
14. Participant has Type 1 diabetes.
15. Participant has uncontrolled Type 2 diabetes, as evidenced by a screening hemoglobin A1c value > 8%.
16. Participant has uncontrolled blood pressure (> 160 mm Hg systolic or > 110 mm Hg diastolic).

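### The 140/90 row in the clinically significant vital-sign count has no change-from-baseline condition and needs both pressures high, so it counts participants who did not worsen and leaves moderate isolated rises uncounted

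*SAP*

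**What the plan says.** SAP 4.7.4 plans two kinds of vital-sign output.

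- **Continuous summaries:** "The actual value and change from baseline (Day 1 Pre-infusion) to each on-study evaluation will be summarized for vital signs". Mean arterial pressure is derived and treated as a vital sign.
- **Participant counts:** "The number and percentage of participants who experience a clinically significant vital sign post-baseline will be summarized". The criteria are introduced with "Clinically significant vital signs will be summarized as follows (increases and decreases are from baseline". The same criteria also decide which results are identified in the by-participant listing.

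Of the seven criteria, the three that concern high blood pressure are:

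- "SBP > 180 mmHg and Increase $\geq$ 20 mmHg"
- "DBP > 105 mmHg and Increase $\geq$ 10 mmHg"
- "SBP $\geq$ 140 mmHg and DBP $\geq$ 90 mmHg"

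The first two require a rise from baseline, and so do the heart-rate increase row and, in the other direction, the three decrease rows. Only the third has no change condition, and it requires both limits at once.

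The entry limit is in Protocol 5.2: "Participant has uncontrolled blood pressure (> 160 mm Hg systolic or > 110 mm Hg diastolic". A participant at or below 160/110 is therefore not excluded on blood pressure.

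**The concern.** The count is of post-baseline clinically significant signs, and its lead-in refers increases and decreases to baseline. A reader will take each row as a count of change. For the 140/90 row that is wrong in two ways. It counts participants who were already at that level and stayed there or improved. Because it requires both pressures, it also passes over a rise confined to one of them.

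Vital signs are part of the primary safety endpoint (Protocol Table 3), and hypertension is among the infusion-reaction signs in Protocol Table 2. SAP 4.7.4 plans no shift table for vital signs; the shift tables in SAP 4.7.3 are for laboratory parameters. The 140/90 row is therefore the only participant-level count of moderate elevation. The listing flag uses the same criteria, so it has the same gap.

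**Working it through.** The plan states no rate, power or sample size for this table, so there is no figure to reproduce. The check has four parts.

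**1. The three high-pressure rows applied literally**

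| Baseline to post-baseline | SBP >180, rise ≥20 | DBP >105, rise ≥10 | 140/90 row |
|---|---|---|---|
| 158/96 to 142/91 (fall) | no | no | **counted** |
| 150/95 to 150/95 (no change) | no | no | **counted** |
| 125/78 to 175/88 (+50 systolic) | no | no | no |
| 115/75 to 139/105 (+30 diastolic) | no | no | no |
| 120/80 to 181/85 | counted | no | no |
| 120/80 to 135/106 | no | counted | no |

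The uncounted zone is an isolated systolic rise to 140–180 with DBP below 90, or an isolated diastolic rise to 90–105 with SBP below 140. Isolated rises above 180 or 105 are caught elsewhere if the rise condition is met.

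**2. Opportunities to be counted**

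Protocol 8.2.2 gives about 7 readings per dosing day: 1 before infusion, 4 during a one-hour infusion, then one at 60 minutes and one at 2 hours. Over 12 infusions, removing the baseline reading and adding Day 8, Month 12 and end of study, this is 12 × 7 − 1 + 3 = 86 post-baseline readings. SAP 4.7.4 has no rule selecting one value per day, unlike SAP 4.7.3 for laboratory data. If all readings count, a participant near 140/90 at entry is likely to be counted at least once.

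**3. Size of the dilution**

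Assume a share *b* meets 140/90 at baseline and all of them are counted, and that the rest have new-onset risk *r*. The observed rate is b + (1 − b)r, and the difference between arms is (1 − b) times the true difference. With assumed risks of 5% on placebo and 15% on active (10 points, ratio 3.0):

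- b = 0.10: 0.10 + 0.90 × 0.05 = 14.5%, against 0.10 + 0.90 × 0.15 = 23.5%. Difference 9.0 points, ratio 1.6.
- b = 0.30: 0.30 + 0.70 × 0.05 = 33.5%, against 0.30 + 0.70 × 0.15 = 40.5%. Difference 7.0 points, ratio 1.2.

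At 36 per arm, b of 10% to 30% is about 4 to 11 participants. Neither *b* nor *r* is in the documents.

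**4. Illustrative simulation**

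Assumptions: true means 120/76 to 135/86, between-person SD 12/9, within-person SD 9/6, correlation 0.6, entry cut at 160/110, and 1 or 14 post-baseline readings.

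- With no drug effect, the share of counted participants who already met 140/90 at baseline was 29% to 47% with one reading and 15% to 30% with 14.
- For an isolated +8 mmHg systolic shift (mean 125/80, 14 readings):

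| Count | No effect | +8 systolic | Contrast |
|---|---|---|---|
| 140/90 row as written | 31% | 42% | 11 points |
| Same row, baseline-negative participants only | 27% | 38% | 11 points |
| SBP ≥140 and rise ≥20, or DBP ≥90 and rise ≥10 | 38% | 57% | 19 points |

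In this scenario the gain comes from the either/or structure. Excluding those positive at baseline changes the contrast very little.

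**The case against.** The strongest reply is that this is one descriptive row, with better tools around it. The same section summarizes change from Day 1 pre-infusion at every evaluation, adds mean arterial pressure and lists each participant by group. Abnormal vital signs that worsen and are judged clinically significant become adverse events (Protocol Appendix 3) and are tabulated under SAP 4.7.2. Added antihypertensives would appear in the concomitant-medication tables of SAP 4.7.5. Randomization balances entry blood pressure apart from chance, and no test or decision depends on the row.

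Most of this stands. A reader might infer that the plan cannot see a blood-pressure effect, that the row is biased between arms, or that it mostly reflects entry blood pressure. The documents do not support the first two, and in every simulated case fewer than half of those counted were positive at baseline, which speaks against the third. An absolute-level row is also a legitimate description. Replacing it would lose cases such as 158/96 to 177/105 (+19/+9), which is counted now but would meet neither a 20/10 rise row nor the >180 and >105 rows.

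The point about participant-level counts remains. A few large rises can be averaged away in a mean. At 36 per arm the 95% half-width for a difference in mean change is 1.96 × SD × √(2/36), which is 4.6, 6.0 or 7.4 mmHg for an assumed SD of 10, 13 or 16. The listing would show a rise in the uncounted zone, but unflagged.

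**Conclusion.** The concern holds in limited form. That the 140/90 row lacks a change condition, counts unchanged or improved participants, and leaves a defined zone of isolated rises uncounted follows directly from the text and rests on no assumption. The consequence is dilution of one participant-level count and its listing flag.

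The size is not determined by the documents. Under the assumed prevalences and risks, a 10-point difference shrinks to between 9 and 7 points. The fall in the ratio from 3.0 to between 1.6 and 1.2 looks more dramatic, but it describes the same dilution. It would be wrong to say that large isolated rises are missed in general, since those above 180 systolic or 105 diastolic have their own rows. This is a small defect that is cheap to correct.

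**What to change.** In SAP 4.7.4:

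1. Keep the 140/90 row, label it as an absolute level, and report it separately for participants who did and did not meet it at Day 1 pre-infusion.
2. Add a row: SBP ≥140 mmHg and increase ≥20 mmHg, or DBP ≥90 mmHg and increase ≥10 mmHg. These are the increments the SAP already uses in its high-pressure rows.
3. Extend the listing flag to the new row.

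The cost is one extra derivation and a few lines of SAP text, with no new data. The new row can have a higher background count: 38% against 31% in the 125/80, 14-reading illustration. At higher assumed means it was about equal (45% for both at 130/83) or lower (51% against 59% at 135/86).
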